### NOTE:

- All visit timings are relative to Day 1. Daprodustat will be dispensed to cover the visit period (plus permitted time window) at each dispensing visit. An IRT transaction will be
  required to dispense daprodustat. Additional IRT transactions may occur to dispense additional daprodustat in case replacement is needed.
- Blood tests for eligibility checked at Screening do not need to be repeated if the Day 1 Visit is performed within 7 days of the Screening Visit.
- All Day 1 procedures will be before the first of dose of daprodustat, except for post dose PK sampling on Day 1 (which occurs at the end of Day 1 once a subject is confirmed as eligible and is enrolled into the study). PK sampling is required for those subjects in the Integrated PK Phase, otherwise PK sampling is optional.
- a. An unscheduled (UNS) /extra check Hgb Visit may be conducted at any time during the study if, in the opinion of the investigator, the subject would benefit from additional monitoring of Hgb and/or other parameters if clinically indicated.
- b. From Week 28, an extra Hgb check Visit should be arranged 4 weeks after the last dose visit if:
  - At the last study visit:
    - there was a dose change
    - if dosing was temporarily withheld as Hgb >12.5 g/dL
    - o a dose reduction was needed but the subject was on lowest dose already
  - Since the last study visit the following occurred:
    - a moderate CYP2C8 was prescribed
    - o a rhEPO or analogue was given in error
    - o a Hgb check performed outside of the study indicates a dose change is needed
  - In the opinion of the investigator the subject would benefit from continued 4-weekly Hab checks;
    - o as the Hgb is at the upper end of the target range
    - waiting 8 weeks for the next Hgb check is considered too long.
- If prolonged QT/QTcF is noted, 2 additional ECG measurements should be obtained and the average QT/QTcF of the triplicate assessment used for eligibility determination. No further ECG monitoring is required, unless as indicated as part of routine care of a subject, see "Electrocardiogram" section of the study protocol.
- d BP and HR will be assessed with using an appropriate size cuff. BP and HR should be preceded by at least 5 minutes of rest for the subject in a quiet setting without distractions. Three consecutive BP measurements will be obtained, of which the median will be recorded.
- Height (or supine length in the very young) and weight will be measured as appropriate for the subject's age and plotted on age and gender appropriate charts as per SoC at the site, see "Physical Examinations" section of the study protocol.
- t. Tanner Staging is not needed if early discontinuation from study intervention, only if an early study withdrawal visit.
- 9 If clinically indicated or required (IRT drug dispensing) at the extra UNS Visit (at any time during the study).
- h. If liver monitoring is required after Day 1, INR should also be performed, see "Liver Chemistry Stopping Criteria" and "Appendix 5: Liver Safety: Required Actions and Follow-up Assessments" sections of the study protocol.
- Pregnancy tests will be conducted using urine, unless estimated Glomerular Filtration Rate (eGFR) ≤15 mL/min/1.73m² when a serum human chorionic gonadotrophin (hCG) is required.
- A total of 3 samples to be collected at 0.5 to 1.5 hour, >1.5 to 3 hour, and >4 hour (maximum 8) time intervals after taking the first dose of daprodustat, which should be taken in the clinic on Day 1, once the subject is confirmed as enrolled in the study having passed screening.

This document is confidential.

SAP Version: SAP V1.0 23-Jan-2025

Controlled Document ID: CCI Effective Date 31-Aug-2020

Filing requirements: TMF

Page 19 of 59

14 July 2025 20

CONFIDENTIAL

214066 Synoptic Report Final

### Statistical Analysis Plan for Interventional Studies

Sponsor: GlaxoSmithKline Research & Development Limited; Protocol No.: 214066/Protocol Amendment 02

k A total of 4 samples to be collected pre-dose, then at 3 time intervals post administration of the daprodustat dose (which should be taken in the clinic on that day) as follows: 0.5 to 1.5 hour, >1.5 to 3 hour, and ≥4 hour time (maximum 8 hour) intervals. It is recommended that the PK samples are taken at Week 2, but flexibility in collecting these 4 PK samples is allowed over the first 2 to 4 weeks provided each sample is collected at a different specified time interval]). If a participant has PK sampling deferred to Week 4, but is put on a dose hold at Week 2 (as the Hgb>12.5 g/dL), then the PK sampling should be delayed until the visit after daprodustat is restarted.

For Argentina ONLY: Pregnancy testing will be performed every 4 weeks for FOCBP as required by local law.

This document is confidential.

21

SAP Version: SAP V1.0 23\_Jan-2025

Controlled Document ID: Effective Date 31-Aug-2020 Filing requirements: TMF

Page 20 of 59

Sponsor: GlaxoSmithKline Research & Development Limited; Protocol No.: 214066/ Protocol Amendment 02

# 5. Endpoints

The protocol indicated that the endpoints would be assessed for each sub-trial (D/ND), overall and by age groups. However, due to early termination of the study, results will be presented by sub-trial (D/ND) but will not be split by age groups.

# 5.1. Primary Safety Endpoint

Incidence of Adverse Events (AEs), Serious Adverse Events (SAEs), Adverse Events of Special Interest (AESIs), and AEs leading to study intervention discontinuation for each sub-trial (D/ND).

# 5.2. Secondary Safety Endpoints

Changes from baseline in laboratory safety parameters, blood pressure (BP), heart rate (HR), height and weight at each time point for each sub-trial (D/ND).

## 5.3. Secondary Efficacy Endpoints

At each study timepoint for each sub-trial (D/ND)

- Hgb values and ESA use (yes/no) at study enrollment
- . Changes in Hgb values from baseline and ESA use (yes/no) at study enrollment
- Incidence of Hgb above, below and within the target range (10 to 12 g/dL) and ESA use (yes/no) at study enrollment
- Daprodustat dose
- · Changes in daprodustat dose from the starting dose

During the course of the study for each sub-trial (D/ND)

· Number of dose changes

# 5.4. Secondary Pharmacokinetic Endpoints

Secondary pharmacokinetic endpoints are listed here but the analysis methods along with TFLs will be described in a separate document.

- PK parameters, including maximum plasma concentration (Cmax) and Area Under the Curve
  (AUC) at steady state will be determined at the end of the study for each dose level overall then
  for each sub-trial (D/ND).
- Plasma concentrations of each pre-defined metabolite at pre-dose (trough) between Week 2 to Week 4, and corresponding Cmax if data permit will be determined at the end of the study for each dose level overall and for each sub-trial (D/ND).

# 5.5. Tertiary Other Health Outcomes of Interest

During the study, the incidence of other health outcomes listed below:

- Related to Hgb and rescue therapy:
  - Use of iron supplements (oral/IV/both)

This document is confidential.

SAP Version: SAP V1.0 23-Jan-2025

Controlled Document ID: Effective Date 31-Aug-2020

Filing requirements: TMF Page 21 of 59

Sponsor: GlaxoSmithKline Research & Development Limited; Protocol No.: 214066/Protocol Amendment 02

- Blood transfusion
- Use of recombinant human erythropoietin (rhEPO) and analogues
- Related to changes in kidney function or intervention:
  - Transplantation
  - Switch between dialysis modalities for D participants only
  - End stage kidney disease (ESKD) for ND participants only
- Other:
  - Death
  - All-cause hospitalization
  - Thrombosis (defined as: vascular access thrombosis, deep vein thrombosis or pulmonary embolism)
  - All-cause loss of vascular access patency.

Responses from Palatability and Acceptability Questionnaire include but limited to:

- Palatability rating (good, acceptable, neither good nor bad, bad, very bad).
- · Ease of swallowing (very easy, easy, neither easy nor difficult, difficult, very difficult).

This document is confidential.

SAP Version: SAP V1.0 23-Jan-2025

Controlled Document ID: CC Effective Date 31-Aug-2020

<sup>1 Unscheduled use of rhEPO or analogues is captured in the endpoint but should not be used as a rescue therapy.

<sup>2 ESKD is defined as at least one of the following:

• an estimated Glomerular Filtration Rate (eGFR), based on the Schwartz equation of <15mL/min/1.73m^2

· new kidney transplantation

the requirement for maintenance dialysis for ≥30 days

Page 23 of 59

Statistical Analysis Plan for Interventional Studies

Sponsor: GlaxoSmithKline Research & Development Limited; Protocol No.: 214066/Protocol Amendment 02

### 6. Analysis Sets

#### 6.1. Screened Set

The Screened Set will include all participants who had a valid Informed Consent Form (ICF) and were screened for eligibility. Participants will be included in the age group based on their age at screening.

#### 6.2. **Enrolled Set**

The Enrolled Set will include all participants who have passed the screening and entered the study. Screening failures (who never passed screening even if rescreened) and participants screened but never enrolled into the study (met eligibility criteria but not needed) are excluded from the Enrolled Set as they did not enter the study.

#### 6.3. Safety Set

The Safety Set (SS) will include all participants who were enrolled and took at least one dose of study medication. The SS will be used for all study population summaries, analyses of safety endpoints, efficacy endpoints and other health outcomes of interest.

#### 6.4. Integrated Pharmacokinetic Set

The Integrated Pharmacokinetic Set (IPKS) will include all participants in the SS who participated in the Integrated PK Phase of the study and who had at least one non-missing PK assessment and who had at least one non-missing post-dose PK assessment associated with an actual study drug administration (non-quantifiable values will be considered as non-missing values). The IPKS will be used for dose decision making during the trial.

#### 6.5. All Pharmacokinetic Set

The All Pharmacokinetic Set will include all participants in the SS who had at least one non-missing PK assessment (non-quantifiable values will be considered as non-missing values) from both Integrated PK Phase and Optional Sampling.

This document is confidential

SAP Version: SAP V1.0 23-Jan-2025

Controlled Document ID: CC Effective Date 31-Aug-2020

Page 24 of 59

Statistical Analysis Plan for Interventional Studies

Sponsor: GlaxoSmithKline Research & Development Limited; Protocol No.: 214066/Protocol Amendment 02

# 7. Primary and Key Secondary Estimands

Primary target estimand and the secondary efficacy target estimand for the study are described in this section. Pharmacokinetic estimand will be described in a separate document.

# 7.1. Primary Estimand

The primary target estimand is the proportion of participants with AEs, SAEs, AESIs, and AEs leading to study intervention discontinuation of daprodustat in children and adolescents with anemia of CKD in each sub-trial (D/ND), regardless of permanent study intervention discontinuation, disruptions or delays in study intervention, intermittent use of rescue therapy or unplanned ESA use.

- Population: Children and adolescent participants with anemia associated with CKD
- Variable: Incidence of AEs, SAEs and AESI from Day 1 to 56 weeks. AEs leading to study intervention discontinuation from Day 1 to 52 weeks of treatment.
- Population-level summary: Proportion of participants with AEs, SAEs, AESI and AEs leading to study intervention discontinuation.
- Intercurrent events:
  - Permanent study intervention discontinuation due to any reason, disruptions and delays in study intervention, intermittent use of rescue therapy and unplanned use of ESA therapy will be addressed using treatment policy strategy, meaning that all safety data will be included regardless of the occurrence of this particular ICE.
  - Kidney transplantation or death will be handled using while-on-treatment strategy, where safety data up to the time of transplantation or death will be used for analysis.
  - For ND participants only, transition to dialysis will be addressed with treatment policy strategy where all safety data will be used regardless of the occurrence of the transition.

# 7.2. Key Secondary Estimand

The secondary efficacy target estimand is the Hgb endpoints at each study time point in children and adolescents with anemia of CKD in each sub-trial (D/ND), regardless of disruptions or delays in study intervention whilst still continuing study intervention (daprodustat) and before any unplanned ESA therapy or rescue therapy.

- Population: Children and adolescent participants with anemia associated with CKD
- Variable: At each study timepoint:
  - Hqb value
  - Change in Hgb value from baseline
  - Hgb above, within and below the target range (10 to 12 g/dL)
- Population-level summary: At each study timepoint:
  - Summary statistics of Hgb value, including number of observed Hgb values, number of missing Hgb values, mean, SD, and median of the observed Hgb values.
  - Mean change in Hgb value from baseline, including number of observed Hgb values, number of missing Hgb values, mean, SD, and median.
  - Number and percentage of participants with Hgb above, below and within the target range (10 to 12 g/dL).
- Intercurrent events:

This document is confidential.

SAP Version: SAP V1.0 23-Jan-2025

Controlled Document ID: CC Effective Date 31-Aug-2020

Sponsor: GlaxoSmithKline Research & Development Limited; Protocol No.: 214066/Protocol Amendment 02

- Disruptions and delays in study intervention will be addressed using treatment policy strategy, where the treatment effect of interest is determined regardless of the occurrence of the ICE and no imputations will be conducted.
- Permanent study intervention discontinuation due to any reason will be addressed using while-on-treatment strategy, where unobserved Hgb results beyond study intervention discontinuation will not be imputed or included for analysis.
- Unplanned use of ESA therapy within the trial will be addressed using while-on-treatment strategy, where the Hgb values will be excluded for the period of 8 weeks following the occurrence of the intercurrent event from analysis and will not be imputed.
- Intermittent use of rescue therapy within the trial will be addressed with while-ontreatment policy strategy, where the Hgb values from the date of initial use of rescue therapy until 8 weeks after the last dose of rescue therapy will be excluded from analysis and will not be imputed.
- Kidney transplantation or death will be handled using while-on-treatment strategy, where
  data up the time of transplantation or death will be used for analysis, no missing Hgb
  values beyond that will be imputed.
- For ND participants only, transition to dialysis will be addressed with treatment policy strategy. All observed data will be used for analysis regardless of the ICE, and missing data will not be imputed.

This document is confidential.

26

SAP Version: SAP V1.0 23-Jan-2025

14 July 2025

Controlled Document ID: CC Effective Date 31-Aug-2020 Filing requirements: TMF

Sponsor: GlaxoSmithKline Research & Development Limited; Protocol No.: 214066/Protocol Amendment 02

#### 8. **General Aspects for Statistical Analysis**

#### 8.1. **General Methods**

- All analyses and outputs will be produced using SAS® version 9.4 or later.
- . Continuous variables will be summarized using the number of observations (n), mean, standard deviation (SD), and median. Categorical variables will be summarized using number of observations (n), frequency and percentages of participants.
- All relevant participant data will be included in listings. All participants entered into the database will be included in participant data listings. The listings will be generally sorted by age group and participant ID for each sub-trial (D/ND), unless otherwise specified. Data collected at unscheduled visits will not be included in summary tables but will be included in data listings.
- Due to study being terminated early, all participants enrolled are from the 12 to <18 years group.
 Unless otherwise specified, all results will be displayed by sub-trial (D/ND) for the 12 to <18 years group only. For PK analysis, results will be displayed overall and by sub-trials (D/ND).

#### 8.2. **Key Definitions**

- Baseline value for any laboratory parameter or vital sign is defined as the last non-missing value prior to the start date and time of the study drug.
- Study day is calculated as the date of event/assessment/specimen collection the first dose of the study drug. One day will be added if resulting study day  $\geq 0$ .
- Duration of any event is defined as end date of the event start date of the event + 1.
- Duration of any event in weeks is defined as (end date of the event start date of the event + 1) / 7, rounded to one decimal place.
- Duration of any event relevant to PK analysis is defined as end date and time of the event start date and time of the event displayed in the format of HHMMSS.
- Change from baseline = post-baseline value baseline value
- Percent change from baseline = (post-baseline value baseline value) / baseline value \* 100
- Pre-treatment phase is defined as any time point prior to the first dose of the study drug, i.e., date <
 date of the first dose.
- On-treatment phase is defined as any time point on or after the first dose of the study drug and on or prior to the last dose of the study drug + 1 day, i.e., date of the first dose ≤ date ≤ date of the last dose + 1 day.
- Integrated PK Phase is defined as the first 4 weeks of dosing in the initially recruited subset of participants in each age group (a minimum of 4 participants per age group; aiming for

This document is confidential

27

SAP Version: SAP V1.0 23-Jan-2025

Effective Date 31-Aug-2020 Controlled Document ID: CC

Page 27 of 59

Statistical Analysis Plan for Interventional Studies

Sponsor: GlaxoSmithKline Research & Development Limited; Protocol No.: 214066/Protocol Amendment 02

approximately 10, 6, 4 and 4 participants for the age groups 12 to <18 years, 6 to <12 years, 2 to <6 years and 3 months to <2 years respectively), during which PK assessments are required.

Post-treatment follow-up phase is defined as any time point within 4 weeks off treatment, i.e., date
of the last dose + 1 day < date ≤ date of the last dose + 28 days.

### 8.3. Missing Data

For the purposes of assessing treatment emergence (defined as the events with a start date on or after the commencement of daprodustat, i.e., Day 1) for AEs or classifying medications into prior/concomitant, the following algorithms will be used for partially missing dates. However, the assessment dates (start date, stop date) without imputation will be presented in the listings.

For start dates of the events:

- Only the year is reported: if the participant received the first dose of study intervention in the
  reported year, date of first dose of study intervention will be used as the start date; otherwise '1
  January' will be used as the start date.
- Only the month and year are reported: if the participant received the first dose of study
  intervention in the reported month and year, the date of first dose of study intervention will be
  used as the start date; otherwise, the first day of the reported month and year will be used as the
  start date.

For stop dates of the events:

- Only the year is reported: if the last visit (including any planned or unscheduled visits) is in the
  reported year, the date of last visit will be used as the stop date; otherwise, '31 December' will be
  used as the stop date.
- Only the month and year are reported: if the last visit is in the reported month and year, the date
  of last visit will be used as the stop date; otherwise, the last day of the reported month and year
  will be used as the stop date.

If an AE has the start date completely missing, this AE will be considered as treatment-emergent, unless the stop date is before first dose of the study intervention.

If a medication has the stop date completely missing, this medication will be considered as ongoing and concomitant.

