## 8.3.1. Time Period and Frequency for Collecting AE and SAE Information

All AEs and SAEs will be collected from the signing of informed consent until the follow-up visit (Week 56) at the time points specified in the SoA (Section 1.3).

All SAEs will be recorded and reported to the sponsor or designee immediately and under no circumstance should this exceed 24 hours, as indicated in Appendix 3. The investigator will submit any updated SAE data to the sponsor within 24 hours of it being available.

Investigators are not obligated to actively seek information on AEs or SAEs after the conclusion of the study participation. However, if the investigator learns of any SAE, including a death, at any time after a participant has been discharged from the study, and he/she considers the event to be reasonably related to the study intervention or study participation, the investigator must promptly notify the sponsor.

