## 10.1.1. Treatment-Emergent Adverse Events

Treatment-emergent adverse events (TEAEs) are those AEs with a start date on or after the commencement of daprodustat (Day 1) regardless of end dates. TEAEs will be summarized separately by SOC and PT. All AEs will be displayed in listings for each sub-trial (D/ND).

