### 10.1.3. Handling of Missing Data

Adverse events with missing start or end dates (for AEs that are not recovering/resolving) will be imputed according to the method described in Section 8.3. The original dates will be shown in listings.

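### SAP 8.3 checks the stop date only when an AE start is completely missing, so an AE with a partial start date that ended before first dose can be counted as treatment-emergent

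*SAP*

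**What the plan says.** SAP Section 8.3 has three rules for incomplete AE start dates.

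- **Year only.** If first dose fell in the "reported year, date of first dose of study intervention will be used as the start date"; otherwise 1 January is used.
- **Month and year only.** The rule turns only on whether dosing began in that month: "intervention in the reported month and year, the date of first dose of study intervention will be" is the operative part. Failing that, the first of the month is used.
- **Completely missing.** "this AE will be considered as treatment-emergent, unless the stop date is before first dose of the study intervention".

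A stop-date condition appears only in the third rule.

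SAP Section 10.1.1 defines TEAEs as "AEs with a start date on or after the commencement of daprodustat (Day 1) regardless of end dates". SAP Section 10.1.3 adds no further check and only points back to Section 8.3: "Adverse events with missing start or end dates (for AEs that are not recovering/resolving) will be imputed according to the method described in" that section.

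Pre-dose events are in the database. Protocol Section 8.3.1 states: "All AEs and SAEs will be collected from the signing of informed consent". Protocol Section 9.3.2.1 says that AEs and SAEs before Day 1 are to be summarized separately.

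**The concern.** Setting an uncertain start to the first-dose date is a sensible conservative default when the event might have begun on treatment. When the stop date is before first dose there is no such doubt, because the event cannot have started on or after dosing. The two partial-start rules still assign it a start on the first-dose date, and the TEAE definition then ignores the end date.

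The three rules also disagree with each other. An AE with no start date and a pre-dose stop is correctly left out of the TEAE counts. If the site adds the month and year, and these match the first dose, the AE goes in. More information gives the worse classification.

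AE incidence is the primary endpoint, and all five AE summary tables in SAP Section 10.1.4 (Tables 3.1 to 3.5) are restricted to treatment-emergent events. A misclassified pre-dose event would sit in those tables, contrary to the separation in Protocol Section 9.3.2.1.

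**Working it through.** The plan states no figure on this point, so there is nothing to reproduce. The check applies the rules as written to worked dates.

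**Inputs**

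- Start, stop and completely-missing rules: SAP Section 8.3.
- TEAE if start is on or after first dose: SAP Section 10.1.1.
- Duration = end − start + 1: SAP Section 8.2.
- First dose 20 Sep 2023: an illustrative date, not taken from trial data.

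| Case | Reported start | Stop | Start imputed by SAP 8.3 | Stop − start + 1 (days) | Class as written | Class with stop-date check |
|---|---|---|---|---|---|---|
| a | Sep 2023 | 12 Sep 2023 | 20 Sep 2023 | −7 | TEAE | pre-treatment |
| b | 2023 | 12 Sep 2023 | 20 Sep 2023 | −7 | TEAE | pre-treatment |
| c | 2023 | Aug 2023, imputed 31 Aug | 20 Sep 2023 | −19 | TEAE | pre-treatment |
| d | Sep 2023 | 25 Sep 2023 | 20 Sep 2023 | 6 | TEAE | TEAE |
| e | Aug 2023 | 12 Sep 2023 | 1 Aug 2023 | 43 | pre-treatment | pre-treatment |
| f | none | 12 Sep 2023 | not imputed | – | not a TEAE | not a TEAE |

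Case c assumes the last visit is not in August, so the stop rule gives the last day of the month. Cases a to c are the defect: each imputed start falls after the stop. Case d shows that the conservative default survives the fix. Case e shows that a partial start in an earlier month is already handled correctly. Comparing a with f shows the inconsistency.

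**When it triggers.** Three conditions must hold together:

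1. the start is partial;
2. its month and year, or its year alone, match first dose;
3. the stop, reported or imputed, precedes first dose.

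A partial stop in the first-dose month does not trigger it, because that stop is imputed to month end or to the last visit.

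Condition 2 is not the rare one. Taking every first-dose date in 2024 and each of the 28 days before it (the full 4-week screening period), 5,376 of 366 × 28 = 10,248 pairs share a calendar month (52.5%) and 9,842 share a year (96.0%). Conditions 1 and 3 together make the case uncommon: the site must know when a short screening event ended but not when it began.

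**Size.** The population PK analysis plan included with the SAP (Section 1.1) gives 4 enrolled participants across both sub-trials. SAP Section 8.1 displays results by sub-trial, and the split is not stated. One participant therefore weighs:

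- 1/4 = 25 points if the sub-trial has 4;
- 1/3 = 33.3 points if it has 3;
- 1/2 = 50 points if it has 2;
- 1/1 = 100 points if it has 1.

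A row moves by that amount only if the participant is not already counted in it. The number of events, which SAP Section 10.1.4 also reports, rises by one in any case.

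**The case against.** The strongest reply is that this is an edge case in a small descriptive report. Screening and Day 1 may be the same day, AE collection begins at consent, and a year-only start for an event inside that window is hard to imagine. The documents do not show that any such record exists among the 4 participants. There is no hypothesis test. Listings show unimputed dates, so an AE with a pre-dose stop could be found in Listing 16.9 by eye. The error runs one way: it can over-attribute a pre-treatment event but cannot hide an on-treatment one.

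All of that stands, and it limits how often the rule misfires and how much harm follows. It does not make the rule correct. The tables would still count the event, and the SAP already accepts the stop-date exception for completely missing starts.

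Three stronger readings are tempting, and the documents do not support them.

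- A reader might infer that screening AEs in general are moved into the treatment period. They are not; an AE with a full start date is untouched.
- A reader might infer that negative durations will appear in the results. SAP Section 8.3 limits the imputation to assessing treatment emergence and classifying medications, and no planned AE table summarizes duration. The −7 and −19 days only show that the imputed start is impossible.
- A reader might infer that one such AE moves overall TEAE incidence by 25 points. That requires all 4 participants to be in the displayed group and the affected participant to have no other TEAE through Week 56.

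**Conclusion.** The point holds in a limited form. As written, SAP 8.3 classes an AE as treatment-emergent when its partial start matches the first-dose month or year, even if its stop date is before first dose. Nothing in SAP 10.1.1, SAP 10.1.3 or the protocol corrects this. It is a stated rule that gives a wrong answer, not a missing detail.

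The likely effect is one participant and one event in a preferred-term or system-organ-class row: 25 to 100 percentage points, assuming a sub-trial size between 4 and 1. Any-TEAE incidence is unchanged unless that participant has no other TEAE. Table 3.2 is exposed in principle only, since an event that ended before dosing is unlikely to be recorded as leading to discontinuation. Whether any record is affected cannot be told from the documents.

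**What to change.** Extend the SAP's existing exception, "unless the stop date is before first dose of the study intervention", to both partial-start bullets in Section 8.3, and name the date to use. Suggested text:

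> If the stop date, reported or imputed, falls before first dose, the AE is classified as pre-treatment. Its start is then imputed as the first day of the reported month, or as 1 January of the reported year when only the year is known.

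In case a this gives a start of 1 Sep 2023 and a duration of 12 − 1 + 1 = 12 days. Stop dates must be imputed before start dates in the program. If first dose was itself on the first day of the reported period, a pre-dose stop contradicts the reported start and the record should be queried.

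The cost is one sentence and one condition in the code. If the tables have already been produced, reading Listing 16.9 for the 4 participants will show whether any record is affected.
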